#### SECTION 1A. RESEARCH STUDY OVERVIEW

#### **Subsection 1A.1 Overview & Introduction**

This three-year study will be a mixed-method, open-label cluster randomized clinical trial to test the benefit of the adapted mindful self-compassion intervention (MSC) at improving primary (PTSD, substance use) and secondary outcomes (depression, anxiety, helplessness, loneliness) among a sample of women experiencing homelessness (WEH) with PTSD/SUD residing in a residential drug treatment site (RDTS). An exploratory aim will be to elucidate mechanisms of treatment-response and maintenance or remission of symptoms.

Phase 1 of this three-year study was completed in December 2023. In Phase 1, a Community Advisory Board (CAB) was created, with women from the RDTS as well as site staff (including clinicians and substance use counselors). The CAB and the UCLA research team jointly created a semi-structured interview guide that was used with four focus groups (total N=27) of trauma-exposed WEH living at the RDTS. The participants completed acceptability and feasibility questionnaires and provided feedback on program design and administration. These suggestions were brought to the CAB and together the study design was finalized accordingly.

Phase II of this study will begin in Winter/Spring 2024. This will be a clinical trial comparing the MSC intervention to treatment as usual (TAU).

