#### 6. BASIC DEFINITIONS

**Mindful Self Compassion (MSC):** is a mind-body integrative health intervention that utilizes meditations, other contemplative practices, home practices, and experiential exercises (including group discussions) to increase SC. To increase feasibility of MSC for use in the RDTS, we will adapt MSC to 7 sessions (6 weekly sessions in alignment with the MSC short course plus the half day retreat included in the full course to facilitate skill consolidation).

**Post-traumatic Stress Disorder (PTSD):** PTSD is a psychological pathology characterized by re-experiencing, avoidance, negative thoughts or cognitions, hyperarousal after experiencing a traumatic event.

**Trauma:** According to the DSM-5, must involve actual or threatened death, serious injury, or sexual violence.

**Arm:** The different groups of the intervention. In this study, Arm 1 is the treatment as usual (TAU) control and Arm 2 is the MSC. Participants are assigned to one Arm or the other, by cohort).

**Cohort:** The group of people that are doing the interventions at the same time.

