**Table 2: Group Assignment Flowchart** 

	Intervention	
	MSC	TAU
Cohort 1	Group 1 (12-14 WEH) Group 2 (12-14 WEH)	
Cohort 2		Group 3 (12-14 WEH) Group 4 (12-14 WEH)
Cohort 3	Group 5 (12-14 WEH) Group 6 (12-14 WEH)	
Cohort 4		Group 7 Group 8
Cohort 5	Group 9 Group 10	
Cohort 6		Group 11 Group 12
Cohort 7	Group 13 Group 14	
Cohort 8		Group 15 Group 16

- b. Informed Consent: Interested and eligible women will complete informed consent at a private location at the RDTS with the PI, a GSR, or a RA. Only the PI and GSR can sign the informed consent so undergraduate RAs may answer questions about the informed consent but final signatures must be obtained from the PI or GSR.
- c. Baseline questionnaire administered:
  - i. After informed consent, participants will complete an assisted psychosocial interview to measure primary outcomes (PTSD and substance use), secondary outcomes (anxiety, depression, hopelessness, ), mediators (emotion-regulation, self-compassion, moral injury, trauma-related guilt, trauma-related shame, craving, mindfulness), and covariates (e.g., negative life

events).

- ii. GSRs and RAs will verbally read questions with response options provided both verbally and on a response card and record responses on iPads using REDCap, accessed through a password. Data will be immediately transferred to UCLA's secure server.
- iii. Women will receive \$15 for completing the baseline assessment.
- d. Locator Guide: This is a critical part of maintaining contact with our participants. However, they may not be inclined to provide all the information on the first or second meeting. NOTE TO RESEARCH ASSISTANTS: PLEASE TAKE THE PICTURE AT THE TIME OF (IMMEDIATELY AFTER) ADMINISTERING INFORMED CONSENT. Note that the picture (like any measure) is optional and participants can refuse the picture and still participate in the study.

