### g. 4-Month Follow-Up

i. Four months after baseline (approximately 2 months after post-assessment), primary and secondary outcomes will be re-assessed, in addition to key covariates and recent negative life events. Participants will be contacted using the Locator Guide and compensated \$30. These sessions will occur in person (at a private location convenient for the participant) or over Zoom as requested by participant.

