#### Mediators & additional outcomes

• Self Compassion Scale (SCS)

This twelve-item scale assesses self compassion on a scale of 1=almost never to 5=almost always. Items will be summed and used as a continuous measure.

• Difficulties in Emotion Regulation Scale

This 18-item scale assesses emotion dysregulation on a scale from 1=almost never (0-10%) to 5=almost always (91-100%). It can be summed up (several items reverse coded) and also has six subscales: Nonacceptance of emotional responses, difficulty engaging in goal-directed behavior, impulse control difficulties, lack of emotional awareness, limited access to emotion regulation strategies, and lack of emotional clarity.

• Mindful Attention Awareness Scale

This is a 15-item scale that assesses mindfulness on a scale of 1=almost always to 6=almost never. It is summed and used as a continuous measure.

Moral Injury and Distress Scale

This six item scale measures moral injury on a scale from 0=not at all to 4=extremely. It is coded categorically (yes moral injury=1, no moral injury=0) and as a continuous outcome.

• Craving

Craving will be measured for alcohol, opioids, methamphetamine, marijuana, psychedelics or other substances (provide name) from 0=no craving at all to 100=maximum possible.

• Trauma-related Shame Inventory

This 24-item measure assesses trauma-related shame from 0=not true of me to 4=completely true for me. It is summed and analyzed as a continuous outcome.

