### **Session 2:** Practicing SC

- o **Topics:** "Resistance & backdraft". How we cause ourselves unnecessary suffering. Development of Safety & Trust. Inner Ally
- o **Key Practices:** Affectionate Breathing. Practicing Loving Kindness. Soles of the Feet. Mindfulness & SC in Daily Life. Here and Now Stone.

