- To evaluate reductions in PTSD symptoms, first, treatment response ( $\geq$  5-point reduction in symptoms) and clinically meaningful improvement (≥ 10-point reduction in symptoms) will be calculated for both immediate and 4-month follow-up. Potential covariates (e.g., demographic indicators; type, timing and amount of trauma exposure, including history of incarceration) will be screened for inclusion (included if p<.05). Change over time will be analyzed, using data from the three time points, using a mixed-effects repeated measures approach. This will also allow for a test of fixed (e.g., treatment group) and random (e.g., cohort) effects over time and conserves power by capitalizing on the longitudinal design. Reductions in PTSD will be examined using a modified Poisson distribution with robust variance, which tends to be less biased than a logit-based approach. Reductions in symptoms (measured continuously) will also be evaluated using a Gaussian distribution. Substance use will be evaluated using the TLFB, quantified as time to first use, days of use and relapse status (abstinent [did not use], lapse [used after study intervention but did not revert to regular use], or relapse [used substances for more than one third of days]). 34,35 Group x time contrasts will be tested. Identical analytic approaches will be used to examine secondary outcomes (suicidality, depression, and anxiety).
- To test for mediation effects, AGReMA (A Guideline for Reporting Mediation Analyses of Randomized Trials and Observational Studies) will be followed. A series of longitudinal structural equation models (SEM) will examine both direct and indirect effects by which change in mediators (emotion regulation, trauma-related guilt, trauma-related shame, moral injury and craving) are associated with change in PTSD, substance use, and secondary outcomes over time. Confidence intervals for indirect effects will be obtained through percentile bootstrap. SEM has the capacity to test for bidirectional

effects between PTSD symptoms and substance use. Model fit (e.g., Root Mean Square Error of Approximation) will be compared to find hypothesized paths that best fit the data.

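### The mediation model leaves out two declared and measured mediators, self-compassion and mindfulness, and includes trauma-related guilt, for which no instrument is listed

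*Combined protocol and SAP*

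**What the plan says.** Subsection 1A.1 states the aim: "An exploratory aim will be to elucidate mechanisms of treatment-response and maintenance or remission of symptoms". The Basic Definitions describe MSC as using "home practices, and experiential exercises (including group discussions) to increase SC", and Subsections 1B.2 and 2.8 repeat that purpose. Mindfulness is also part of the course content: Session 2 in Subsection 2.8 lists "Mindfulness & SC in Daily Life" among its key practices.

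The candidate mediators appear in three kinds of place:

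- **Declared.** Subsection 2.2, item 2c (baseline questionnaire), gives "mediators (emotion-regulation, self-compassion, moral injury, trauma-related guilt, trauma-related shame, craving, mindfulness". Footnote c to the assessment overview (Table 3 in Subsection 2.3) names the same seven.
- **Measured.** Subsection 2.7 describes six instruments, and Subsection 2.10 repeats the six for the post-assessment. Of the Self Compassion Scale it says: "This twelve-item scale assesses self compassion on a scale of 1=almost never to 5=almost always". The Mindful Attention Awareness Scale is also there. No guilt scale appears in either list.
- **Modelled.** The mediation paragraph of Section 3 plans longitudinal structural equation models for "change in mediators (emotion regulation, trauma-related guilt, trauma-related shame, moral injury and craving".

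For the 4-month visit, Subsection 2.2, item 2g, says that "primary and secondary outcomes will be re-assessed, in addition to key covariates and recent negative life events". The assessment overview in Subsection 2.3 marks that visit with the mediator footnote in both arms.

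**The concern.** A mechanism analysis of a self-compassion programme would be expected to ask first whether the programme changes self-compassion, and whether that change carries the effect on PTSD symptoms and substance use. The planned models do not ask this, although the data are to be collected. They do include a guilt pathway for which no data are scheduled.

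Two features of Section 3 make the list matter more than it would in a loosely exploratory analysis. First, the sample size of 162 is attributed partly to guidelines for testing mediation, so mediation helped to shape the design. Second, model fit is to be compared to find the paths that best fit the data. If self-compassion and mindfulness enter the models only at that stage, their inclusion becomes a choice made after seeing the data.

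The guilt gap is of a different kind. An omitted variable that was collected can be added by changing a list. A variable that was never collected cannot be recovered.

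**Working it through.** No power, alpha or sample-size figure bears on this point. The check compares the three lists.

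| Construct | Declared (2.2 item 2c; 2.3 footnote c) | Instrument (2.7; 2.10) | In the models (Section 3) |
|---|---|---|---|
| Emotion regulation | yes | Difficulties in Emotion Regulation Scale, 18 items | yes |
| Trauma-related shame | yes | Trauma-related Shame Inventory, 24 items | yes |
| Moral injury | yes | Moral Injury and Distress Scale, 6 items | yes |
| Craving | yes | rating from 0 to 100 by substance | yes |
| Self-compassion | yes | Self Compassion Scale, 12 items | **no** |
| Mindfulness | yes | Mindful Attention Awareness Scale, 15 items | **no** |
| Trauma-related guilt | yes | **none listed** | yes |
| Total | 7 | 6 | 5 |

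- In all three lists: 4.
- Measured but not modelled: 2 (self-compassion, mindfulness).
- Modelled but with no instrument: 1 (guilt).
- Cross-check: 4 + 2 = 6 measured; 4 + 1 = 5 modelled; 4 + 2 + 1 = 7 declared.

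**Is the Section 3 list closed?** It reads so. The same part of Section 3 marks its covariates, fixed effects, random effects and fit indices as examples, but not its mediators. Section 3 names no other analysis of self-compassion or mindfulness and gives no reason for leaving them out.

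**Could a guilt measure stand elsewhere?** The citations attached to the six instruments (references 8 to 13) are one per instrument, and none is for a guilt scale. The shame inventory is described as measuring shame only.

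**How many indirect paths are involved?** Section 3 relates the mediators to PTSD, substance use and the secondary outcomes. It names three secondary outcomes (suicidality, depression, anxiety), which makes 2 + 3 = 5 outcomes. One path per mediator and outcome, before counting time points, gives:

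- As written: 5 mediators × 5 outcomes = 25 paths. Of these, 1 × 5 = 5 run through guilt and have no listed data, which leaves 20.
- Added by self-compassion and mindfulness: 2 × 5 = 10.
- With guilt deleted: 6 × 5 = 30.
- With guilt kept and measured: 7 × 5 = 35.

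Counting instead the seven outcome measures in Subsection 2.7 (PCL-5, AUDIT, DAST, hopelessness, anxiety, depression, loneliness), the addition is 2 × 7 = 14. Ten is therefore the lower count.

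**4-month visit.** The table in Subsection 2.3 gives the mediators three time points: baseline, post-intervention and 4 months. If the text of item 2g were taken as complete, they would have two.

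**The case against.** The strongest reply is that the aim is labelled exploratory, that no primary or secondary comparison of MSC with TAU depends on it, and that self-compassion and mindfulness are already declared as mediators and scheduled. All of this stands. Their omission loses no data and can be mended by wording, which limits the seriousness of the point.

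It may also be said that Subsection 2.7 groups these scales as mediators and additional outcomes, so the two missing ones could be meant as outcomes. The heading leaves that room, but Subsections 2.2 and 2.3 both call them mediators.

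For guilt, one could look to neighbouring content: the shame inventory, the moral injury scale, or the blame symptom among the PTSD criteria that the PCL-5 covers. The plan assigns none of these to guilt, and the last is part of the outcome itself.

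Three stronger readings are tempting, and the documents do not support them:

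- *The mechanism aim cannot be answered.* Four of the five modelled mediators have instruments, so part of it can.
- *No mediators will be collected at 4 months.* Item 2g is a brief summary that does not exclude them, and the assessment table schedules them. Even with two time points, mediator change from baseline to post-intervention could be related to 4-month outcomes; only later mediator change would be lost.
- *The plan makes self-compassion the lead mediator.* The documents do not rank the mediators. Giving it priority would be reasonable from the definition of MSC, but it is a preference and is not needed to cure the inconsistency.

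**Conclusion.** The point holds as an inconsistency that should be fixed. Of seven declared mediators, four can be analysed as planned, two are measured but left out of the models, and one is in the models without a listed measure. Followed as written, the trial does not test whether MSC works through self-compassion, the construct it is defined as increasing, or through mindfulness. Its guilt pathways, five on the count of outcomes named in Section 3, have no listed data. The treatment comparisons on primary and secondary outcomes are untouched.

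This rests on two readings: that the mediator list in Section 3 is complete, as its wording indicates, and that the batteries in Subsections 2.7 and 2.10 are the full set of scales administered. If a guilt scale is in use but was not written down, that part reduces to a documentation gap. The 4-month text is a matter of alignment only.

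**What to change.** 1. In the mediation paragraph of Section 3, list self-compassion (Self Compassion Scale), mindfulness (Mindful Attention Awareness Scale), emotion regulation, trauma-related shame, moral injury and craving. Do this before analysis.
2. Delete trauma-related guilt from Section 3, from Subsection 2.2 item 2c and from footnote c of the assessment table in Subsection 2.3. If it is to be kept, name a guilt measure in Subsections 2.7 and 2.10 while data can still be collected.
3. In Subsection 2.2 item 2g, state that the mediators are repeated at 4 months, to agree with the assessment table.

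The first change is wording only, because both scales are already scheduled. Its price is at least 10 further indirect paths, which should be reported as exploratory with the number examined stated. Deleting guilt costs nothing in data collection; keeping it adds a questionnaire to each assessment, and women enrolled before the change would lack a baseline value.

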#### **SECTION 2. INTERVENTION DELIVERY**

#### **Subsection 2.1 - Phase II Overview**

In Phase II, we will assess the benefit of MSC to produce improvements in primary (PTSD, SUD) and secondary outcomes (depression, anxiety, hopelessness, loneliness) compared to Treatment as Usual (TAU) and to explore mechanisms of symptom change over time. We will implement an open-label cluster randomized clinical trial of an adapted MSC course for PTSD/SUD with WEH (N=202), randomized to MSC (n=101) or TAU (n=101). Women will be recruited from Prototypes, a HealthRIGHT 360 RDTS. Inclusion criteria will be: 1) woman age 18 and over; 2) probable PTSD as judged by the PCL-5 (score of 31 or higher, indicated as having optimal signal detection); 3) no cognitive impairment according to a score of < 10 on the Short-Blessed Test; 4) experienced homelessness in the past 6 months or prior to incarceration ("spent night in public or private shelter or on the street"); and 5) able to speak and understand English. We will recruit 8 cohorts of 24-26 WEH and each cohort will be divided into 2 groups. Cohorts of participants will be randomized to an adapted MSC course or TAU prior to enrollment of the first participant and randomization will occur at the level of the cohort rather than the participant. This is to minimized contamination in cohorts as women live together at the RDTS but cycle out after ~3 months. Women receiving MSC or TAU will complete psychosocial questionnaires, demographics, and a Locator Guide at baseline. Women receiving MSC will participate in weekly MSC classes for 6 weeks, followed by a post-intervention follow-up and 4-month follow-up. Women receiving TAU will complete short psychological surveys each week for 6-weeks, followed by a 6-week post-baseline and 4-month follow-up.

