### 2. Group Assignment and Intervention Procedure

a. Cohorts of participants will be randomized to an adapted MSC course or TAU prior to enrollment of the first participant. Consistent with the cluster design, randomization will occur at the level of the cohort rather than the participant. This design was chosen to avoid contamination within the cohorts, since participants

reside at the same RDTS. There will be eight cohorts in total, each with two intervention groups of 12-14 WEH. Each cohort will receive the same intervention (e.g., in Cohort 1 there will be two groups of MSC, in Cohort 2 there will be two groups of TAU). See **Table 2** below:

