# Section 3 – Data analytic plan

• *Power analysis*. Sample size was estimated using G\*Power and standard guidelines for testing mediation,  with α=.05, β=.80, and the standard deviation bound at ±1.91. Effect size estimates were derived from prior research on SC interventions for PTSD, which found a small-medium effect size (Cohen's d=0.2-0.5).  Particularly since the effect of MSC to reduce PTSD symptoms is emerging research, findings have been mixed regarding effect sizes for direct and indirect effects of SC interventions on PTSD, with some studies finding large effects of reduced PTSD due to SC interventions,  and others finding medium effect sizes.  (Of note, few randomized trials have been conducted).  To account for additional covariates, the clustering design,  and Type 1 error due to multiple tests, a small-medium effect size of .3 was conservatively estimated. Sample size appropriate for mediation was derived from a percentile bootstrap method, which simulations consistently show to be the most powerful test compared to similar methods (e.g., Sobel, bias-corrected bootstrap).  This yielded a final sample size of 162. Based on the team's prior research, we conservatively estimate 80% retention over time for a target enrollment of 202, for a total of 8 cohorts of 24-26 participants (divided equally into two groups per cohort). In the

team's prior work, 82% of those screened were eligible for participation: thus, we will aim to screen 246 WEH.

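### The percentile-bootstrap intervals for indirect effects make no provision for cohort, although whole cohorts are randomized, four per arm

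*Combined protocol and SAP*

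**What the plan says.** Under Group Assignment and Intervention Procedure (Subsection 2.2), "randomization will occur at the level of the cohort rather than the participant". Table 2 there shows eight cohorts, alternating between MSC and TAU, four per arm.

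The mediation bullet in Section 3 plans longitudinal structural equation models linking change in five named mediators (emotion regulation, trauma-related guilt, trauma-related shame, moral injury, craving) to PTSD, substance use and the secondary outcomes. On uncertainty it says "Confidence intervals for indirect effects will be obtained through percentile bootstrap" and does not mention cohort.

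Clustering is recognised in three other places in Section 3:

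- **Outcome analysis:** the mixed-effects repeated-measures model offers cohort as a random effect.
- **Statistical analysis, opening paragraph:** propensity scores, multilevel models with cohort as a random effect, or both, may be used for covariates that differ between cohorts at baseline.
- **Power analysis:** clustering is one of several reasons for the planning effect: "a small-medium effect size of .3 was conservatively estimated".

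The power analysis also ties the sample size to mediation: "Sample size appropriate for mediation was derived from a percentile bootstrap method", and then "This yielded a final sample size of 162". No ICC or design effect appears anywhere.

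**The concern.** An indirect effect is the product of two paths: treatment to mediator (a) and mediator to outcome (b). Because cohorts are allocated, path a compares four cohorts with four. Anything the women of a cohort share, such as group dynamics, season or staffing at the site, adds variance to a. Resampling women one at a time does not reproduce that variance, so the interval for the product is too narrow whenever path a dominates its uncertainty.

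The risk is a specific wrong conclusion. A mediator that predicts outcome, such as shame or craving, may differ between arms because of which cohorts fell where, and be reported as a mechanism of MSC. The plan examines several mediators against several outcomes, so the error applies to each pair.

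**Working it through.** **Inputs from the documents.** Eight cohorts, four per arm (Table 2); 162 analysed, so 162/8 = 20.25 per cohort; 202 enrolled, so 202/8 = 25.25; arms "randomized to MSC (n=101) or TAU (n=101"); planning values "with α=.05, β=.80, and the standard deviation bound at ±1.91", with .80 read as power; effect size .3.

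**Assumptions, not in the documents.** ICC from 0 to .10 in mediator and outcome; one continuous mediator and one continuous outcome; two-sided 95% intervals; a = 0 for error rates; b as stated below.

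**The plan's own figure.** The documents state no error rate for mediation, so the only figure to reproduce is 162, and it does not follow from the stated .3. For a participant-level percentile bootstrap with independent women:

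- both standardized paths .3: 80% power needs about 122-128, and 162 gives 92%;
- group difference d = .3 and b = .3: 162 gives 47%, and about 350 are needed;
- 162 gives 81% if both paths are .26, a value the documents do not contain.

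The inflation does reproduce: 162/0.80 = 202.5, against 202 stated. The derivation of 162 is a separate matter. It matters here only because it shows no clustering adjustment that could be checked.

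**Closed form for path a.** The true variance of the estimate is the participant-level variance times DE = 1 + (m − 1) × ICC. When b is clearly non-zero, the interval for ab excludes zero about as often as the interval for a does, so

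false-positive rate ≈ 2 × [1 − Φ(1.96/√DE)].

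With m = 20.25:

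| ICC | DE | 1.96/√DE | Closed form | Simulated, b about .3-.4 |
|---|---|---|---|---|
| 0 | 1 | 1.960 | 5.0% | about 5-6% |
| .01 | 1.1925 | 1.795 | 7.3% | 7-9% |
| .02 | 1.385 | 1.665 | 9.6% | 8-11% |
| .05 | 1.9625 | 1.399 | 16.2% | 15-20% |
| .10 | 2.925 | 1.146 | 25.2% | 24-27% |

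The simulated column is the participant-level percentile bootstrap at N = 162 with a = 0; repeat runs agree to within about a percentage point. Raising b to .59 gives 8.8%, 10.2%, 19.5% and 24.2% at ICC .01, .02, .05 and .10. With all 202 women analysed, the rates are about 8%, 10-12%, 19-20% and 29-32%.

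**Width.** At N = 162 and b of .3 or more, the bootstrap SD is 0.85-0.93 of the true SD at ICC .02 and 0.60-0.62 at ICC .10.

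**Where inflation is small or absent (N = 162).**

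- a = 0, b = 0: at most 2% at every ICC.
- a = 0, b = .14: 2-9%.
- b = 0 with a real path a (d = .6): 5-6% if cohort effects on mediator and outcome are independent, rising to about 15% only if they are strongly correlated (.9) at ICC .10.

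**Resampling cohorts instead.** Drawing the four cohorts per arm with replacement gives about 12-16% false positives when b is .3-.39, even at ICC 0. Four units per arm are too few for a percentile bootstrap.

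**A cohort-respecting interval.** Path a from the difference in cohort means (t, 8 − 2 = 6 df), path b from regression within cohort, and 4,000 Monte Carlo draws of the product. With b = .39, false positives are 4.7%, 5.5% and 5.3% at ICC .02, .05 and .10.

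**Its power** at N = 162 and ICC .05: about 20% for d = .3, b = .3, and about 57% for d = .6, b = .3.

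**The case against.** The strongest reply is that the plan is silent rather than wrong. It never says that women are the resampling unit, and it names cohort random effects elsewhere. Mechanisms are an exploratory aim (Subsection 1A.1), and the inflation depends on an ICC and a path b that the documents do not give.

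Much of this stands. The resampling unit is unstated, and participant-level resampling is an inference from an unqualified bootstrap. But silence does not rescue the rule, because resampling the eight cohorts also fails. The other cohort provisions do not help either. The random effect belongs to the outcome model. The baseline-imbalance clause is optional and could be met by propensity scores alone. A smaller planning effect changes N, not the width of an interval. An exploratory 95% interval should still have about its stated coverage.

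A reader might infer that mediation claims in general carry a 9-27% error rate. The documents do not support that. The rate needs a cohort ICC of about .02 to .10 and a mediator that predicts outcome but is not moved by treatment.

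A reader might also infer that 162 was derived for independent women. The text says that clustering influenced the choice of .3 and does not show the derivation. What can be said is that no ICC or design effect is stated.

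**Conclusion.** The gap is real: as written, the rule for indirect-effect intervals does not respect the unit of randomization, and it misstates uncertainty under either reading of the resampling unit. Under the assumptions in the working, error per pair runs from 7-9% at ICC .01 to 24-27% at ICC .10, against a nominal 5%. The omission is certain. The size is conditional, because ICC and path b are assumed and the simulation covers one continuous mediator and outcome, not the full longitudinal SEM.

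It would go too far to conclude that the plan ignores clustering altogether, or that the comparison of MSC with TAU on the primary outcomes is undermined by this point. The outcome model has its own cohort provision. The consequence is confined to mechanism claims. It should be corrected before those analyses are run.

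**What to change.** For continuous mediators and outcomes, replace the bootstrap sentence in Section 3 with:

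> The treatment-to-mediator path is estimated at cohort level (difference in cohort means or equivalent, t with 6 df) and the mediator-to-outcome path within cohort. 95% intervals for the indirect effect come from Monte Carlo sampling of the two estimates. Participant-level bootstrap intervals are not used for inference.

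The SEM can stay for describing bidirectional paths between PTSD and substance use. The product of two linear coefficients does not carry over directly to time to first use or three-level relapse status. For these and other non-continuous substance-use outcomes, specify a cohort-respecting method suited to the outcome, or report indirect effects descriptively.

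In the power analysis, state that no ICC or design effect entered the derivation of 162, or show the one that did.

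The cost is plan wording and a short program, with no change to recruitment, visits or data. The price is wider intervals and low power, so the exploratory mediation aim should be described as unlikely to detect modest indirect effects with eight randomized cohorts.
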